5.3 EXPLORATORY ENDPOINTS

The exploratory objectives of the study are to evaluate the effect of nalbuphine HCl ER tablets on:

- The potential of nalbuphine HCl ER tablets to impact on the measurement of nerve fiber density (histology) and MOR/KOR density (histology, Western Blot), as well as histological (H&E) changes in skin biopsies taken at Baseline and the final Treatment Period Visit when compared to biopsy material assessed during study TR03 (optional procedure at select sites only).

6 NUMBER OF SITES AND PATIENTS

Up to 10 sites in the North America and Europe are planned to participate in this study. Eligible patients who have successfully completed the TR03 study and wish to participate in TR03ext may be enrolled, treated, and analyzed. The maximum number of patients will not exceed the number of patients who complete the TR03 study (i.e., up to 60 patients).

7 ESTIMATED STUDY DURATION

The total study duration for any individual patient will be up to 53 weeks. Patients will receive drug treatment for up to 50 weeks, followed by a two week washout period.

8 SELECTION CRITERIA

8.1 STUDY POPULATION

Patients with prurigo nodularis who completed the TR03 study and have met Inclusion/Exclusion eligibility requirements for TR03ext (see [Section 8.2](#) and [Section 8.3](#)).

8.2 INCLUSION CRITERIA

Patients must meet all of the following criteria to be eligible:

1. Have been adequately informed of the nature and risks of the study and have given written informed consent by Visit 1a.
2. Have completed participation in the TR03 study.

Completion of participation in the TR03 study is defined as completion of Study Drug treatment through TR03 Visit 5 and completion of the TR03 Visit 6.

3. Agree to comply with the contraception requirements as below:

Female patients of childbearing potential are required to use one barrier method (e.g., condom, cervical cap, or diaphragm) of contraception in addition to one other method (e.g., intrauterine device [IUD], hormonal contraception, tubal ligation, Essure procedure, or spermicide).

For the purpose of this study, all females are considered to be of childbearing potential unless they are post-menopausal (i.e., at least 1 year since last menses and age >50 years) or surgically sterile (i.e., tubal ligation, hysterectomy and/or bilateral oophorectomy).

4. Ability and acceptance to provide written informed consent.
5. Willing and able to comply with study requirements and restrictions
6. Agree to the confidential use and storage of all data (including photography) and use of all anonymized data for publication including scientific publication.

8.3 EXCLUSION CRITERIA

If a patient meets any of the following criteria, he or she is *not* eligible:

1. Patients with a history of congestive heart failure of Class 2 or higher as graded using the New York Heart Association scale (scale provided in [Appendix 5](#))
2. Patients with a history of angina pectoris grade 2 or higher as graded using the Canadian Cardiovascular Society grading scale (scale provided in [Appendix 5](#))
3. History of ventricular tachycardia, torsade de pointes, family history of sudden death, myocardial infarction or acute coronary syndrome within the previous 3 months, as reported by the patient.
4. Serum potassium below the laboratory lower limit of normality. Potassium supplementation can be prescribed and the serum potassium level repeated
5. QTcF interval >450ms on screening EKG
6. Heart rate <50 BPM on screening
7. Use of a medication known to be associated with risk of torsade de pointes (see [Section 9.7.8](#), Safety Assessments, for hyperlink to the CredibleMeds Filtered QTDrug List for cardiovascular related prohibited medications with a known associated risk of Torsade de Pointes)
8. History of substance abuse within the past year as determined by the Investigator
9. Significant medical condition or other factors that in the opinion of the Investigator may interfere with the conduct of the study
10. Known hypersensitivity or allergy to nalbuphine or formulation components
11. Is a pregnant or lactating female.

9 STUDY PLAN

9.1 GENERAL STUDY DESIGN

This is an open label extension study for patients who have completed the TR03 study.

9.2 RATIONALE FOR STUDY DESIGN

The primary objective of this TR03ext study is to evaluate the safety of nalbuphine HCl ER tablets in patients with prurigo nodularis for up to 50 weeks on drug, followed by a two week washout period for a total of up to 53 weeks of study duration. The open label design allows all patients, who have completed the parent study TR03, an opportunity to receive active treatment for the assessment of the safety of nalbuphine HCl ER tablets over a longer term and follow the effect of skin lesion healing in addition to reducing itch. A maximum of 50 weeks on study drug was chosen as a reasonable time frame that would add substantially to the understanding of chronic use of nalbuphine HCl ER tablets chronic use in prurigo nodularis.

Metze et al (1999) reported that 9 out of 17 patients with PN who were treated with the mu antagonist medication naltrexone reported a decrease in pruritus intensity of at least 50%.

Reduced scratching as well as skin lesion healing was reported over a time period of up to 20 months on drug. Based on these clinical observations, TR03ext was designed to be of sufficient duration to observe potential anti-pruritic suppressive effects of study drug on scratching behavior and thus potentially skin lesion healing. Furthermore, the TR03ext study design anticipates potential sustained anti-pruritic effect that may outlast the actual dosing of study drug in TR03. Thus an Observation Period has been incorporated to follow patients whose Worst Itch NRS has been significantly reduced for up to 12 weeks in order to measure the durability of the anti-pruritic effect and to allow patients to receive study drug if pruritus intensity increases within the 12 week time period.

This study will also allow evaluation of a titration algorithm that mimics the manner in which opioid medications are often used in clinical practice (i.e., stepwise titration) to a tolerable dose with an improvement in worst itch intensity. To facilitate evaluation by achieved dose, the dose to which the patient has been titrated at the end of Treatment Week 4 will be maintained through Study Week 50, with the exception of two allowable down-titration (See [Table 3](#) for dosing schedule). Patients who require a third down-titration after Treatment Week 4 must be discontinued from the study.

Patients can enroll into TR03ext and receive drug as early as approximately 2 weeks following their last dose of study drug in the parent study TR03. Approximately one-third of patients are expected to enter the study after having received placebo in TR03. These patients are expected to have a high level of pruritus intensity. On the other hand, some patients who have received active treatment in TR03 may still have either reverted to their original pruritic conditions or may have a residual anti-pruritic effects from the drug treatment even following the 2-week wash out period. To allow for various starting levels of pruritus intensity, patients who have Worst Itch NRS that is ≥ 5 will enter the Treatment Period upon completion of Visit 1a. Patients whose Worst Itch NRS score is < 5 will be entered into an extended screening period, no-treatment criteria Observation Period for up to 12 weeks or until they develop a higher level of pruritus (i.e., Worst Itch NRS ≥ 5), at which point they will transition to the Treatment Period upon completion of Visit 1b. All patients entering the Treatment Period, whether immediately upon study entry or following a period of time in the Observation Period, will initially be titrated to a dose that can be as high as 180 mg BID during the first 4 weeks of the Treatment Period (See [Table 3](#) for dosing schedule). Patients who continue in the Observation Period and maintain a Worst Itch NRS score of < 5 will be screen failed from the study at the end of the 12-week period. While patients remain in the Observation Period, they will not be considered as enrolled into the study, but as participating in an extended screening process until they are eligible for treatment.

Patients who fail to improve, as defined by the failure-to-improve criteria, will be taken off study drug treatment. A failure-to-improve criteria is implemented beginning on TV 3 and at every subsequent Treatment Visit, and is described in [Section 11.1](#). The rationale for the failure-to-improve criteria is based on the following: Following a maximal titration period of up to 3-weeks, an approximate 2-week window on stable drug dose should be sufficient for the drug to start eliciting a beneficial effect. The subject's self-reporting of pruritus intensity at each visits beginning at TV 3 will be compared to the baseline value of the patient's pruritus intensity upon entry to TR03ext. The premise of the failure-to-improve criteria is that patients will not be allowed to continue to receive study drug for an extended

period of time if there is no demonstration of diminishment in pruritus intensity. Subjects discontinued from treatment are to participate in the Washout and Safety Follow-up Period, unless consent is withdrawn. These patients will also receive a Telephone Contact 30 days (+2 weeks) post the completion of study drug to collect safety information related to previous drug exposure.

In the parent study, TR03, the two target doses (90 mg and 180 mg) of nalbuphine HCl ER are both within the dose range that was well tolerated in HD subjects and healthy volunteers subjects from study TR01 (30 mg to 240 mg BID for up to 15 days). Additionally, data from TR01 suggested a decrease in itching intensity in this dose range. Further, the safety profile of nalbuphine following injection is well documented. Injectable nalbuphine has been commercially available in the United States since 1979 and there has been marketing experience within the European Union dating back to 1986 (See Nalbuphine -Medicines Evaluation Board in the Netherlands Public Assessment Report (2010) for a recent review).

In order to facilitate analysis of the clinical safety data and efficacy data, patients in the present study will begin titration at the 30 mg QD dose and titrate to only a maintenance dose ranging between 30 mg BID and 180 mg BID. The 30 mg BID and 60 mg BID doses are believed to be only marginally effective doses based on available TR01 data. However there is a two time dose reduction permitted for all subjects during Treatment Weeks 5-50 (see [Table 3](#)) to the next lower allowed dose (e.g., a subject at the 90 mg BID maintenance dose will be permitted a dose reduction to 60 mg BID or subsequently to 30 mg BID and then be maintained at that dose level for the remainder of the study).

The study population being evaluated is an intended target population for oral nalbuphine HCl ER tablets: prurigo nodularis patients.

Patients will be closely monitored for safety. All patients will be seen at the Investigator site (See [Schedule of Events in Appendix 1](#)). Adverse events and vital signs will be recorded. Additionally, 12-lead ECGs (locally and centrally read), physical examinations, and clinical laboratory testing will be conducted to monitor safety on patients receiving study drug. Safety monitoring will be done to address the primary objective of evaluating the longer term safety of study drug exposure. The primary endpoint is a description of adverse events during up to 50-weeks of treatment with nalbuphine HCl ER tablets. An important secondary endpoint objective of the study is to use recorded PAS metrics to assess the study drug anti-pruritic suppression of the scratching behavior of the subject and impact on skin lesion improvement. Changes in patient-reported outcome measures: Worst itch NRS, Average itch intensity NRS, VRS (itchy, burning and stinging), ItchyQoL, MOS Sleep-R, HADS and PBI-P will be explored.

9.3 SAFETY MONITORING PLAN

Patients will be closely monitored for safety. Adverse events will be continuously evaluated throughout the study (and in particular AEs of special interest: nausea, vomiting, constipation, somnolence, sedation, dizziness, and vertigo) and vital signs, locally and central cardiac core laboratory read 12-lead ECGs, physical examinations, and clinical laboratory testing will be conducted to monitor patient safety.

An independent Data Safety Monitoring Board (DSMB) will periodically review safety data. The frequency of data review and DSMB processes are outlined in the DSMB charter.

Patients with apparent failure-to-improve to a stable dose of study drug will be taken off study drug.

As with all subjects who are discontinued from study drug, the patient will complete a daily SOWS scale for the two weeks following the last dose of study drug. The SOWS is a self-administered scale for grading opioid withdrawal symptoms. If the subject is experiencing any symptoms on the SOW scale to a moderate degree, the subject will be instructed to contact the site. If a subject is determined to be experiencing significant subjective withdrawal symptoms (at the Investigator's discretion), the subject will be offered treatment.

As summarized in Section 6.2.7 of the Investigator Brochure, the CNS has been identified as the only target organ when nalbuphine was given to animals at high doses. In addition, the most frequently reported adverse events reported in the nalbuphine HCl ER tablet dosing studies were primarily in the nervous system and gastrointestinal organ system categories. .

To mitigate opioid-related side effects, nalbuphine will be titrated over 4 weeks based on tolerability to a dose that is between 30 mg BID to 180 mg BID (see [Table 3](#)). Titration is a clinical management strategy consistent with dosing of opioids in general (Jovey 2003). The titration regimen planned in this study is similar to the regimen used in study TR01, in which doses in the planned range were well tolerated ([Section 3.3.2](#)) except uptitration is not a forced titration. This will provide flexibility for each patient to assess tolerability. In this study, the combination of a low starting dosing (30 mg on the first day) followed by a relatively slow titration (dose escalation after a minimum of six consecutive doses over approximately 3 days) is expected to minimize treatment-limiting opioid adverse effects. See [Table 3](#) for the drug titration scheme. The time interval between dose escalations is consistent with the "three day tolerance check" suggested by the National Opioid Use Guideline Group of Canada (2010) for outpatient clinical practice management of opioid drug titration as part of monitoring patient side effects.

Nalbuphine has μ -opioid antagonist pharmacological properties. To minimize the possibility of acute opiate withdrawal occurring at drug initiation in a physically dependent subject, patients receiving daily doses of opiates are excluded from the study. Patients who require ongoing non-daily opiates concurrently with nalbuphine should be monitored carefully for additive opiate effects. If patients develop a new need for daily opiates during the study, the Investigator is required to contact the Medical Monitor to discuss the specifics of the situation.

It is known from prior studies, that gastrointestinal opioid-like adverse effects (e.g., nausea, vomiting, and constipation) occur early and can be treatment-limiting. In anticipation of the possible occurrence of these effects, pre-medications for nausea will be permitted and Investigators will be advised to use pharmacologic or non-pharmacologic means to avoid constipation as clinically indicated. In anticipation of the possible occurrence of central nervous system (CNS) AEs such as somnolence, patients will be instructed to be aware of possible CNS AEs that may occur. The evening doses during the Titration Period should

be taken at home. The first dose of any new titration step will occur with an evening dose (see [Table 3](#)). In order to monitor any potential CNS related side effects, a brief neurological assessment will be conducted at each study visit as well as a focused neurological medical history will be obtained at enrollment.

Patients will be additionally instructed that if any significant CNS AEs occur, they are to avoid activities such as driving and operation of dangerous machinery until the effect of the Study Drug can be assessed by the Investigator. Additionally, concomitant use of daily opioids during the course of the study, other than for short-term use, can be undertaken with the approval of the Medical Monitor. Overdoses or opioid-related significant central nervous system adverse effects may be reversed with opioid antagonists if clinically indicated.

Although psychological dependence or abuse can develop to chronically administered opioid drugs, the risk for psychological dependence or abuse in this study is judged to be low based on previous clinical studies with nalbuphine HCl ER oral tablets. To date, there have been no reported cases of psychological dependence or abuse reported following dosing for 3 weeks up to 180 mg BID and dosing for 15 days up to 240 mg BID. See the Investigator Brochure for details. Nevertheless, the nalbuphine HCl injection package insert for the product sold in the United States states that “*individuals with a prior history of opioid or other substance abuse or dependence may be at greater risk for the development of drug abuse and dependence*”.

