9.6.4 Transition to Treatment Period (Visit 1b)

Confirm each patient's eligibility (see [Sections 8.2](#) and [8.3](#)) prior to performing any Visit 1b procedures. If the patient does not meet eligibility requirements, do not perform any Visit 1b procedures; the patient is to be screen failed.

See [Table 4](#) for summary of Visit 1b procedures.

Patients evaluated at OV 2-4 who record a Worst itch NRS greater than or equal to 5 (≥ 5) and, are otherwise eligible, can immediately begin Visit 1b. This patient then transitions into the Treatment Period and will undergo the following procedures:

- obtain vital signs
- conduct a physical examination
- collect central laboratory samples (hematology and chemistry)

- collect serum pregnancy sample in women of childbearing potential (done at the central laboratory)*
- collect urine for central lab urinalysis
- urine for pregnancy (must be confirmed negative prior to dispensing study drug)*

* If the urine pregnancy test result is negative and the serum pregnancy test result is positive, the patient is to be contacted and the following actions are to take place:

- instruct the patient to discontinue taking study drug
- schedule the patient for an unscheduled visit to collect another serum pregnancy test

The serum pregnancy test result will be used to determine the patient's eligibility to continue receiving study treatment. See [section 17.5.2.1](#) regarding how pregnancies are to be handled in this study.

- obtain blood for PK
- Perform 12-Lead ECG after at least 5 minutes in a supine position (See the Study Reference Manual for ECG procedures, [section 17.4](#) Electrocardiograms for the handling of Cardiovascular adverse events)
- administer PRO measurements:
 - Average itch intensity NRS
 - VRS
 - ItchyQoL
 - MOS Sleep-R
 - HADS
 - PBI-P

The PRO questionnaires must be administered at the study site under the supervision of and by trained study staff, strictly adhering to PRO Administration Instructions (see Study Reference Manual).

- record AEs
- review of concomitant medications, including over-the-counter medications, nutritional supplements, and vitamins
- complete the PAS
- dispense Study Drug to the patient required until return at Treatment Visit 2, TV2
- instruct patients to self-administer the first dose on the evening of Visit 1b at home

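### Section 9.3 says daily opiate users are excluded, but the eligibility lists that sites are told to check (8.2, 8.3 and the synopsis) do not contain that exclusion

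*Protocol*

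**What the plan says.** All references are to Version 2.0 of the protocol (Amendment 1).

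- Section 9.3 notes nalbuphine's mu-antagonist action and the risk of acute withdrawal when it is started in a physically dependent patient. To limit that risk, "patients receiving daily doses of opiates are excluded from the study". Patients with ongoing non-daily opiate use may take part under careful monitoring. A new need for daily opiates during the study must be discussed with the Medical Monitor.
- Section 8.1 defines the population as TR03 completers who "have met Inclusion/Exclusion eligibility requirements for TR03ext", and points to Sections 8.2 and 8.3 for those requirements.
- Section 9.6.1 lists confirmation of eligibility as a Visit 1a procedure. Section 9.6.4 tells sites to confirm eligibility against 8.2 and 8.3 "prior to performing any Visit 1b procedures".
- Both visits include a concomitant-medication review. At Visit 1b it is worded as "review of concomitant medications, including over-the-counter medications, nutritional supplements, and vitamins".
- Treatment then starts away from the site. The Visit 1b text is "instruct patients to self-administer the first dose on the evening of Visit 1b at home", and Visit 1a has the equivalent instruction.

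**The concern.** Section 9.3 speaks of the exclusion as if it were already in force, but the lists that put exclusions into force do not carry it. A site that works through 8.2 and 8.3, as 8.1 and 9.6.4 direct, would find nothing that makes a daily opiate user ineligible. The opiate would appear in the medication review, but no listed criterion turns that record into a screen failure.

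The harm is the one the sponsor names, acute withdrawal at initiation. Section 3.1.3.2 also states that nalbuphine can induce opioid withdrawal. The first dose is taken at home in the evening. The next scheduled contact is a telephone call in Treatment Week 2 (Section 9.6.2.1.1), and the next visit is in Treatment Week 3 (Section 9.6.2.1.2). The opiate withdrawal scale is scheduled from the End of Treatment Visit onward or at Early Termination (Section 9.7.8), so it does not cover initiation. That leaves the entry exclusion as the main planned protection against this event.

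**Working it through.** The plan gives no figure to reproduce here. The check is a count of the criteria and a reading of each one, followed by a reading of the opioid text elsewhere.

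**Inclusion criteria (Section 8.2), 6 items:** informed consent by Visit 1a; TR03 completion; contraception; ability to consent; compliance; agreement to data use. Items naming opiate or opioid use: 0.

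**Exclusion criteria (Section 8.3), 11 items:** heart failure; angina; arrhythmia, infarction or family history of sudden death; low potassium; QTcF; heart rate; torsade-risk medication; substance abuse; significant medical condition or other factors; hypersensitivity; pregnancy or lactation. Items naming opiate or opioid use: 0.

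**Total:** 6 + 11 = 17 criteria, and 0 + 0 = 0 name daily opiate use. The synopsis repeats the same lists with the same omission.

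**Nearest items:**
- Inclusion 5, "Willing and able to comply with study requirements and restrictions", is general and does not name opiates.
- Exclusion 7 depends on torsade risk. It would catch an opiate user only if the particular drug were on that list.
- Exclusion 8, "History of substance abuse within the past year as determined by the Investigator", concerns abuse. A patient on prescribed daily opiates need not meet it.
- Exclusion 9, "Significant medical condition or other factors that in the opinion of the Investigator may interfere with the conduct of the study", lets the investigator exclude such a patient but does not require it.

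**Opioid text elsewhere:**
- A later paragraph of Section 9.3 allows daily opioids beyond short-term use in the course of the study with the Medical Monitor's approval.
- Section 9.7.6.3 asks for caution when opiates are initiated, for Medical Monitor contact if an enrolled patient needs them daily, and for discontinuation if an opioid is introduced with more than 2 weeks of use expected.

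These provisions govern opioid use during the study. Neither says that a patient already taking opiates daily at Visit 1a or 1b is ineligible, so neither replaces the missing criterion.

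**Effect on the primary endpoint:** Section 5.1 describes treatment-emergent events in Treatment Weeks 5–50. Withdrawal at initiation would occur in Treatment Week 1, outside that window.

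**The case against.** The strongest reply is that the exclusion is in the protocol. Section 9.3 states it without qualification and gives the reason, and it binds the investigator as much as 8.3 does. Inclusion 5, and the consent text in Section 9.6 about agreeing to study restrictions, tie entry to rules stated elsewhere. Dosing a daily opiate user would be a protocol breach. A reader might infer from the lists that the protocol makes such patients eligible. That does not follow, because the 9.3 sentence rules it out.

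Nor is the period after consent uncontrolled. Section 9.7.6.2 has every medication and its reason recorded from consent onward, and tells patients not to take new medications without consulting the investigator. Section 9.3 requires Medical Monitor contact for a new daily opiate need and does not limit this to enrolled patients. The matching sentence in 9.7.6.3 does refer to enrolled patients, and Section 9.6.3 says that patients in the Observation Period are not yet enrolled, so that sentence alone would not reach them.

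A reader might also argue that the time since the last TR03 dose, or placebo treatment in TR03, measures the exposure. The documents do not support this. TR03's own opiate rules are not shown, Visit 1a is itself the last TR03 visit, and earlier tolerance of nalbuphine says nothing about current opiate use.

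These replies lower the severity of the point. They do not remove the mismatch: the check that sites are directed to make would pass a patient whom 9.3 says must not be dosed.

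**Conclusion.** The inconsistency is real and should be fixed. Section 9.3 states a safety exclusion that appears in 0 of 17 eligibility criteria and not in the synopsis. The design decision to exclude is clear. The fault is that it is missing from the lists that define eligibility.

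The number of patients affected is unknown. The documents give no prevalence of daily opiate use, and the limit of 60 patients is only the size of the study. That the number is small is a judgement, resting on the binding sentence in 9.3, the medication reviews before dosing and the investigator's discretion under exclusion 9.

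Two stronger readings should be resisted. A reader might infer that the main safety result is biased, but the Weeks 5–50 window excludes events at initiation. A reader might also object that Section 9.6.4 puts the eligibility check ahead of the medication review. Both come before dispensing and the evening dose, so the order alone does not expose a patient.

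The conclusion assumes that the Version 2.0 sections not at hand (after the heading of Section 10.2, including Appendix 1) do not supply the criterion.

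**What to change.** Add current daily opiate use as a numbered exclusion in Section 8.3 and in the synopsis. State that it is checked against the concomitant-medication review at Visits 1a and 1b before study drug is dispensed.

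The cost is one criterion entered in two places. No new procedure is needed, because the medication review already takes place at both visits. Any patient excluded by it is one whom Section 9.3 already means to exclude.
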